2.2.3 Intervention Group

Phase 1 (Titration)

Baseline Visit

Patients assigned to the intervention group will meet with a DCES and receive insulin therapy education according to current standard of care procedures (e.g., how to use an insulin pen, when and where to administer insulin, etc.). Whereas DCESs typically provide patients with written titration instructions prepared by the physician provider, for the intervention, DCESs, another HCP and/or a trained clinical research coordinator will train patients to use MDC-T for titration guidance. The physician provider will prepare an individualized titration algorithm, including a dose plan and dose adjustment rules that will be embedded in MDC-T. The DCES, another HCP, and/or clinical research coordinator will demonstrate to the patient how to use the MDC Titration Module to determine and guide dosing adjustments.

All patients will be asked to complete a baseline survey to assess behavioral and psycho-social factors that may influence diabetes self-management. In addition, patients will receive a threemonth supply of insulin pens (Lantus (U100) Solostar Pen or Toujeo (U300) Solostar Pen, as per treating Physician).

Patients will be instructed to return for a three-month follow-up clinic visit, as is standard of care for patients new to insulin.

Month 3 Visit

At the three-month appointment, the DCES or another HCP will assess the patient's experiences with titration and MDC-T, which will be documented using a study-specific survey. If the patient successfully reached their glycemic target, they will be invited to participate in Phase 2 of the study (maintenance).

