A majority of the data is also expected to be available within the EMR for the control group. HbA1c, FBG, blood pressure, cholesterol, and BMI data should be recorded and accessible for patients. In addition, many patients also have BG meter readings. At a minimum, we will select patients who have HbA1c values that correspond to baseline [index date = date of insulin initiation] and follow-up time points/time frames that correspond with those described in the study calendar (section 2.2.5). EMR records, including notes, downloads, and related documented data will be reviewed to identify and classify hypoglycemic events according to already aformentioned definitions.

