3 HUMAN SUBJECTS

3.1 Subject Population

Intervention participants will be identified in a consecutive manner at participating UPMC community-based PC practices, outpatient clinics and inpatient units. Study participants will include adult male and female T2DM patients, 18 to 75 years old, with T2DM and suboptimal glycemic control (HbA1c > 7.5%) who are recommended to start titrating basal insulin and willing and able to use the MDC app.

The retrospective comparative group will be selected from eligible patients who previously were treated at the UPMC Diabetes Outpatient Clinics. This group will be chosen for two reasons. First, patients seen at the Diabetes Outpatient Clinic have the most robust data available regarding insulin titration, including HbA1c and FBG and, for many patients, BG meter readings. Secondly, this particular group establishes a standard of specialty care against which to compare MDC and will uniquely inform the benefit of MDC. Patients in the usual care group will be identified using EMR data accessed through the UPMC Clinical Data Warehouse.

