3.2.2 Usual Care Group

- Adult male and female patients 18 to 75 years old
- HbA1c > 7.5%
- Started on basal insulin in a UPMC Diabetes Outpatient facility within the past three years of study start

• Has blood glucose data available in EMR (At least two HbA1c measurements corresponding to baseline and a subsequent time point after insulin titration) FBG readings)

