10 WITHDRAWAL OF SUBJECTS

Participation in this research is completely voluntary. An individual's decision whether or not to participate in this research, or to later withdraw from it, will not affect his/her current or future medical care at UPMC or the relationship with the University of Pittsburgh. If a participant chooses to withdraw, any information collected about the participant up until the time of withdrawal will be kept, but no additional information will be collected.

Study investigators may choose to remove participants from the study if a participant is advised by their health care provider to discontinue insulin therapy or if a participant is no longer able to act independently to follow study procedures due to such reasons as mental/cognitive incapacity or moved to assisted living.

In addition, a subject may be considered "lost to follow" if they cannot be reached. Every attempt will be made to contact these participants and after 3 failed attempts a certified letter will be sent to the participant.

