11.2 Payments

Patients will receive \$20 for completing the baseline survey and \$50 for each completed survey at 3 and 6 months. In addition, \$100 per participant will be allotted for HCPs as remuneration for their time spent on study-related activities (e.g., consenting participants, survey administration, instructing patients on MDC, etc.).

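### Controls are selected on HbA1c recorded after the index date, on one reading including a 6-month value that no stated analysis uses; intervention patients face no such condition

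*Combined protocol and SAP*

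**What the plan says.** The primary endpoint (section 2.5.1) is change in HbA1c at 3 months against usual care. Two sections say which usual care patients may supply that comparison.

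- Section 2.4.1, Control Group: "At a minimum, we will select patients who have HbA1c values that correspond to baseline" (the date of insulin initiation), and also at "follow-up time points/time frames that correspond with those described in the study calendar". The study calendar (section 2.2.5) has follow-up at 3 months (±2 weeks) and 6 months (±4 weeks).
- Section 3.2.2 makes this an inclusion criterion: "At least two HbA1c measurements corresponding to baseline and a subsequent time point after insulin titration". It gives no window for the later value.

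For the intervention group, section 3.1 says: "Intervention participants will be identified in a consecutive manner". The criteria in section 3.2.1 require no later HbA1c. Section 2.2.3 adds: "Patients will be instructed to return for a three-month follow-up clinic visit", and describes that visit as standard of care. For a patient who cannot be reached, section 10 provides that "after 3 failed attempts a certified letter will be sent to the participant". After a withdrawal no further information is collected.

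Section 2.6.2 matches 1:1 on a propensity score from age, gender, baseline BMI and baseline HbA1c, with race and number of comorbid conditions optional. Sections 2.6.1 and 2.6.2 give no missing-data method, and no rule for a matched pair whose intervention member has no 3-month HbA1c.

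**The concern.** Whether a patient becomes a control depends on what happened after insulin was started. Patients who left care, or were not retested at the required time, are never counted. Intervention patients enter at baseline whatever happens later.

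If starters who stay in care and are retested change differently from those who do not, the control mean is not the mean for comparable starters. The matching variables are all measured at baseline and none describes attendance, so matching cannot repair a selection made afterwards. The error would fall on the primary endpoint. A larger sample would not reduce it, and the confidence interval would not show it.

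The two control rules also leave the outcome time unsettled. Under section 3.2.2 alone, a control's follow-up HbA1c could fall at any time after titration, yet be compared with a 3-month intervention value.

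**Working it through.** **1. The plan's own figure.** Inputs from section 2.6.1: SD of 3-month change 1.5, 109 patients per arm; 95% confidence from section 2.6.2.

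Half-width = 1.96 × 1.5 × √(1/109 + 1/109) = 0.398 (0.400 with the t distribution on 216 df). The stated ±0.40 reproduces and is not in dispute. It assumes 109 evaluable patients in each arm. Controls meet that by construction; the intervention arm may not.

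**2. The control rules side by side.**

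| | Section 2.4.1 | Section 3.2.2 | Intervention (3.2.1) |
|---|---|---|---|
| Baseline HbA1c | required | required | required (above 7.5%) |
| Later HbA1c for entry | at calendar follow-up times (plural) | one, after titration | none |
| Timing of later value | as the calendar | no window | visit at 3 months ±2 weeks |

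A control who meets section 2.4.1 also meets the HbA1c part of section 3.2.2, but not the reverse.

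**3. Is a control's 6-month value used?** Section 2.1 defines Phase 2 for intervention patients who reach target, and section 2.6.2 analyses it in the intervention group only. The Phase 2 endpoints (section 2.5.2.2) name no comparison with usual care. The generalized estimating equations sentence in section 2.6.2 speaks of slopes in the two groups without naming time points, but the only between-group binary HbA1c endpoint listed in section 2.5 is at 3 months. So no stated analysis needs the value.

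**4. Bias formula.** In one group, at given matched baseline values, let f be the share of starters without the required later HbA1c, and g the mean change in those observed minus the mean change in those not observed. The all-starter mean is (1 − f) × observed mean + f × unobserved mean = observed mean − f × g. The observed mean is therefore off by f × g. If both groups are analysed on observed values and g is equal:

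size of net bias = (f_control − f_intervention) × g

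Requiring a 6-month value as well as a 3-month value can only raise f_control.

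**5. Numbers, all by assumption.** The documents give neither f nor g.

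- 30% against 10%, g = 0.25: 0.20 × 0.25 = 0.05 points.
- 30% against 10%, g = 1.0: 0.20 × 1.0 = 0.20 points, half of the 0.40 half-width.
- 30% against 30%, equal g: 0.
- Equal shares do not cancel if g differs: with 20% in both groups and g of 0.25 and 0.50, the bias is 0.20 × 0.50 − 0.20 × 0.25 = 0.05.

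**6. Precision if controls are matched before outcomes are seen.** Assume 15% or 40% of 109 controls lack the outcome, leaving 93 or 65.

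- 109 against 93: 1.96 × 1.5 × √(1/109 + 1/93) = 0.415.
- 109 against 65: 1.96 × 1.5 × √(1/109 + 1/65) = 0.461.
- If broken pairs are dropped: 0.431 with 93 pairs, 0.516 with 65 pairs.

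**The case against.** The strongest reply is that follow-up is much the same in both groups. Section 2.2.3 calls the 3-month visit standard of care and the 6-month visit a routine clinic visit, and the study calendar lists lab work under clinical care and EMR abstraction. The payments (section 11.2) are made "for each completed survey at 3 and 6 months", and section 2.2.3 allows surveys electronically or by mail, so they need not bring a patient in for a blood test. An analysis of observed values would also condition the intervention group on having a 3-month HbA1c. All of this stands. A reader might infer that intervention HbA1c comes from research follow-up and control HbA1c from chance attendance; the documents do not support that. What clearly differs is the tracing in section 10.

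Secondly, a reader might say that section 2.4.1 certainly demands a 6-month value, or that it contradicts section 3.2.2. Neither is established. The plural in section 2.4.1 points to both calendar times, but the text is loose, and the two sections differ in how specific they are rather than being incompatible. They still need to be aligned, because they define different control pools and different outcome times.

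Thirdly, the choice of comparator rests partly on its data being the most complete (section 2.2.4). That is a fair reason to choose the clinics. It does not justify excluding, uncounted, those patients within them who lack a later value.

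**Conclusion.** The point holds as a moderate design weakness. Control eligibility uses information from after the index date, intervention eligibility does not, and baseline matching cannot correct for it. The part most easily removed is the 6-month condition, if section 2.4.1 is read as imposing it: it adds selection on staying in care and serves no stated analysis. The missing window in section 3.2.2 is a separate gap that bears on the same endpoint.

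The size is not known. The 0.05 to 0.20 points rest on assumed unobserved shares of 30% and 10%, an equal g of 0.25 to 1.0 points, and analysis of observed values in both groups. The direction is not known either. If the controls left out improved less than those kept, the app's benefit is understated; if HbA1c was repeated mainly in patients doing badly, it is overstated.

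A reader might quote a larger figure by multiplying the control share left out by g alone, for example 0.40 × 0.6 = 0.24 points. That is a gross shift on assumed inputs. It ignores the matching loss in the intervention group and should not be read as the bias in the comparison.

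**What to change.** Put one rule in sections 2.4.1 and 3.2.2:

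- Controls for the Phase 1 comparison do not need a 6-month HbA1c.
- The outcome is the HbA1c nearest 3 months after the index date, within a stated window that is the same in both groups. A narrow window leaves more routine-care patients unobserved, so choose the width before outcomes are seen.
- Identify eligible controls from data available at the index date. Report, by group, how many lack a 3-month HbA1c.
- In section 2.6.2, state one rule for missing 3-month values that applies to both groups and covers broken matched pairs. Add inverse-probability-of-observation weighting or multiple imputation as a sensitivity analysis. State that either works only if baseline data explain who is observed; neither removes selection on unmeasured behaviour.

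Dropping the 6-month condition and fixing the window costs almost nothing. Counting the controls without an outcome needs a little more EMR extraction and analysis. Matching before outcomes are seen has a real price: a half-width of about 0.42 to 0.46 instead of 0.40 if 15% to 40% of 109 controls lack the outcome, and more if broken pairs are dropped. If that is too much, controls can still be matched among those with a 3-month value, provided the number left out and their baseline characteristics are reported.

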2.4.2 Health Care Provider/Clinical Workflow-Related Outcomes

Clinician experiences and perspectives on insulin dosing previous to the study will be collected at baseline and the usability of and satisfaction with the MDC will be assessed through a study-specific satisfaction survey (provider version). DCESs will keep logs detailing experiences (including triage/escalation to the need for an endocrinologist visit) and logistical issues, particularly those related to technology and disruption of workflow. In addition, at the end of the study, discussions s will be organized with UPMC HCPs and staff to review study findings and elicit additional perspectives on effective ways to integrate the app into clinical workflow in clinical practice.

2.4.3 Patient-Related Outcomes

Patient usability of MDC to titrate insulin and maintain glycemic control will be tracked relying on the devices inherent data analytics. Patient satisfaction will be assessed using study specific acceptability and satisfaction surveys (patient version) and the validated Diabetes Medication System Rating Questionnaire-Short Form (DMSRQ-SF) [20]. Diabetes medication system refers to the medication taken as well as the devices and supplies required to administer the medication. The DMSRQ-SF includes 20 items to assess convenience, negative events,

interference, self-monitoring of blood glucose burden, efficacy, social burden, psychological well-being, treatment satisfaction and treatment preference [20].

Other patient data to be collected will include demographics, diabetes-related information (e.g., duration, medications, etc.), and their level of diabetes distress, which will be evaluated at baseline and follow-up with the 17-item Diabetes Distress Scale (DDS17). The DDS17 assesses four dimensions of distress – emotional, regimen, interpersonal and physician [21], and has shown a consistent pattern of relationships with HbA1c, diabetes self-efficacy, diet and physical activity in multiple samples of patients with T2DM [22].

2.5 Study Endpoints

2.5.1 Primary Endpoint

Change in HbA1c at 3 months as compared to patients using standard of care.

2.5.2 Secondary Endpoints

2.5.2.1 Phase 1 (Titration)

- Change in HbA1c from baseline to 3 months within and between groups
- Proportion of patients reaching HbA1c <7% at 3 months as compared to patients using SOC
- Change in FPG from baseline to 3 months within and between groups
- Patient-reported changes in behavioral and psychosocial outcomes from baseline to 3 months (survey)
- Patient-reported acceptability of and satisfaction with MDC-T (survey)
- Provider-reported acceptability of and satisfaction with MDC-T (survey)
- Rate of escalation to Endo (Endocrine visits) for patients using MDC-T
- Safety end points (including hypoglycemia, any untoward adverse events)
- Number and type of technical complaints

2.5.2.2 Phase 2 (Maintenance)

- Proportion of patients maintaining their individualized HbA1c goal at 6 months as compared to the number of patients at target HbA1c at start of maintenance phase (month 3)
- Proportion of patients maintaining HbA1c <7% at 6 months compared to number of patients at target HbA1c <7% at start of maintenance phase (month 3)
- Change in HbA1c from baseline and 3 months to 6 months
- Change in FPG from baseline and 3 months to 6 months, if available
- Adherence to HCP recommended treatment plan
- Patient-reported changes in behavioral and psychosocial outcomes from baseline or 3 months to follow up time points (survey)
- Safety end points (including hypoglycemia, AEs)

• Number and type of technical complaints

2.6 Statistical Analysis

2.6.1 Power and Sample Size Justification

The primary objective of this study is to estimate the difference in HbA1c between the study treatment groups at 3 months. The sample size justification is based on precision estimate (i.e., confidence interval for the HbA1c difference between groups). The expected standard deviation for the 3-months change from baseline in HbA1c is 1.5. With 109 patients in the interventional arm and 109 patients in the retrospective control arm, the treatment effect, expressed as the LS means difference between arms, would be estimated with an expected precision of \pm 0.40. Additionally, this sample size allows for a sufficient number of patients after drop-out, loss to follow-up and/or missing data to enter the maintenance phase (Phase 2) of the study. Based on previous research and experiences with insulin titration, an anticipated 70% of patients (n=76) will enter Phase 2 of the study.

2.6.2 Data Analysis

Patients will be matched 1:1 on a propensity score based on baseline demographics and clinical characteristics to improve the comparability of the interventional and retrospective groups. A logistic regression model will be used to estimate the propensity score and those baseline variables that influence treatment assignment will be included in the model. In this analysis, the following variables will be used to calculate the propensity score: age, gender, baseline BMI and baseline HbA1c. Other factors that may be included are race and number of comorbid conditions. Once the propensity score is calculated, a greedy nearest neighbor algorithm will be used for matching to form pairs of subjects from intervention and control groups with similar propensity scores. This means that for a given treated subject, the closest untreated subject within the specified caliper distance is selected for matching to the treated subject.

Descriptive statistics (e.g., demographics, duration of diabetes, etc.) will be used to describe the study groups. Baseline comparisons will be examined using standardized mean differences. A linear mixed model will be used to adjust the fixed effect of baseline FBG and the random effect of matched pairs, allowing to estimate the treatment effect with 95% CI. . Generalized estimating equations (GEE) for binary outcomes will be for binary outcomes to compare the change in slopes of outcomes of interest between the two groups and account for matched pairs . In addition, for the intervention group only, descriptive statistics will be used to summarize other data (e.g., patient and provider surveys, MDC metrics, etc.), and thematic analysis of any qualitative findings will be made.

Phase 1 (Titration): For the intervention group only, using a descriptive statistical approach, a primary assessment of titration outcomes will be built into the study at 3 months to evaluate the MDC-T app using a combination of clinical data, provider and patient feedback and process data (including patient/provider study-specific efficiency and satisfaction surveys, DE logs, validated DMSRQ-SF and MDC analytics).

Phase 2 (Maintenance): For the intervention group only, using a descriptive statistical approach, an assessment of maintenance outcomes will occur to compare the percentage of patients at goal between the study treatment group at 6 months. Clinician and patient experiences and perspectives on the usability of and satisfaction with MDC-M will be assessed through various means including study-specific efficiency and satisfaction surveys.

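### Diabetes duration and baseline glucose-lowering medication are named in neither the propensity score nor the outcome model of a non-randomised comparison; both should be prespecified as adjustment variables.

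*Combined protocol and SAP*

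**What the plan says.** Section 2.6.2 (Data Analysis) describes 1:1 matching on a logistic-regression propensity score. It opens with a general rule, "those baseline variables that influence treatment assignment will be included in the model", and then gives the list for this study: "the following variables will be used to calculate the propensity score: age, gender, baseline BMI and baseline HbA1c". Two more variables are left open: "Other factors that may be included are race and number of comorbid conditions". No rule says when they go in.

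For the outcome, "A linear mixed model will be used to adjust the fixed effect of baseline FBG and the random effect of matched pairs". No other covariate is named.

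Duration appears in 2.6.2 only as a descriptor: "Descriptive statistics (e.g., demographics, duration of diabetes, etc.) will be used to describe the study groups". Medication does not appear there at all. Yet section 2.4.3 plans to record both, "Other patient data to be collected will include demographics, diabetes-related information (e.g., duration, medications, etc", and the patient-history footnote of the study calendar (2.2.5) lists both at baseline.

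On precision, section 2.6.1 states: "The expected standard deviation for the 3-months change from baseline in HbA1c is 1.5". With 109 patients per arm it expects a precision of ±0.40 for the difference between arms.

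**The concern.** Section 2.1 describes a non-randomised trial with a prospective intervention group and a retrospective usual-care group. Matching and model adjustment are the only protection against confounding. The arms are also selected differently. Section 3.2.1 requires intervention patients to be willing and able to use the app, a requirement that 3.2.2 does not list for controls, and the controls started insulin in an earlier period.

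How long a patient has had diabetes, and what treatment they already take when basal insulin starts, could plausibly differ between such groups and relate to the HbA1c response. If a difference remains after matching on the four named variables, the primary 3-month estimate will carry it as if the app had caused it. The 95% interval reflects sampling error only and would not show it. As written, the descriptive table could display an imbalance in duration while the estimate stays unadjusted for it.

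**Working it through.** **1. Reproduce the plan's precision.** Inputs from 2.6.1: SD 1.5 and n = 109 per arm. The 95% level is from 2.6.2.

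- SE = 1.5 × √(2/109) = 0.203
- Half-width = 1.96 × 0.203 = 0.398, which agrees with ±0.40.

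This figure contains no allowance for residual confounding.

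**2. Closed-form illustration.** The inputs here are assumptions, because the documents give none. Let d be the standardized mean difference (SMD) of an omitted covariate after matching, and r its partial correlation with HbA1c change.

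- Bias b = d × r × SD
- Coverage = Φ(1.96 − b/SE) − Φ(−1.96 − b/SE)

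| Case | b | b / 0.40 | Coverage |
|---|---|---|---|
| One covariate, d 0.2, r 0.1 | 0.2 × 0.1 × 1.5 = 0.03 | 7.5% | about 94.7% |
| One covariate, d 0.3, r 0.2 (central) | 0.3 × 0.2 × 1.5 = 0.09 | 22.5% | 92.7% |
| One covariate, d 0.5, r 0.3 | 0.5 × 0.3 × 1.5 = 0.225 | 56% | 80.2% |
| Two covariates, same direction, each d 0.3, r 0.2 | 2 × 0.09 = 0.18 | 45% | 85.6% |

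For the central case, b/SE = 0.09/0.203 = 0.443, so coverage is Φ(1.517) − Φ(−2.403) = 0.927. If baseline HbA1c and fasting glucose explain 30% of the variance, the residual SD is 1.5 × √0.7 = 1.255 and the central bias is 0.3 × 0.2 × 1.255 = 0.075. The SE shrinks in the same proportion, so coverage does not change. Two covariates acting in opposite directions would offset each other.

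**3. Does adding fixed effects remove the bias?** This was simulated with:

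- 109 treated patients and pools of 200, 300 or 600 controls (the documents do not give the pool size);
- eight independent normal covariates with SMD 0.3 before matching;
- greedy 1:1 matching with a caliper of 0.2 SD of the logit;
- baseline HbA1c and fasting glucose explaining 30% of the variance, and a true effect of zero;
- 600 runs per cell (Monte Carlo error about 0.008 on bias and 0.01 on coverage).

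The SMDs here are before matching, whereas those in step 2 are after it. Ranges are over the three pools.

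| Omitted covariates | Plan as written: bias, coverage | Four-variable score plus fixed effects: absolute bias, coverage |
|---|---|---|
| One, SMD 0.3, r 0.2 | 0.06–0.09, 91.5–94.0% | at most 0.015, 93.7–95.8% |
| Two, each SMD 0.3, r 0.2, same direction | 0.141–0.162, 83.7–87.5% | at most 0.013, 94.0–94.5% |

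The fixed effects widened the half-width by less than 0.01. Repeating the two-covariate case with ordinary least squares in place of the random-pair model gave slightly milder figures for the plan as written: bias 0.14–0.15 and coverage 87–90%.

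**4. Sensitivity to the independence assumption.** If duration correlates 0.4 with age and both are imbalanced in the same direction, matching on age lowers the SMD for duration from 0.30 to about 0.19, and the bias falls by rather more than a third. If the imbalances run in opposite directions, matching on age raises the bias.

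**The case against.** **The general rule could admit both variables.** It could in principle. But the next sentence gives the list for this analysis, and they are not on it. If the rule is meant to reach further, the adjustment set stays open until someone decides, and that also needs settling. Section 2.2.4 refers to the Statistical Analysis Plan for matching details; 2.6.2 is the only analysis text in the combined document. If another text lists these variables, the point falls.

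**The variables may not be available for controls.** This stands in part. Section 2.4.1 ties the study calendar to the intervention group, and its control paragraph does not name duration or medication. A reader might infer that usable control data are being ignored, but the documents do not establish that. Availability is likely: 2.2.1 lists medications in the data warehouse, and 2.6.2 expects to describe the groups by duration. It is not secured, so the fix starts with a check.

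**Eligibility already narrows the differences.** Sections 3.2.1 and 3.2.2 share the age range and the HbA1c threshold, and both arms are starting basal insulin. This limits the imbalance but does not remove it.

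**The size is assumed and the central case is modest.** This stands in full. Coverage near 80% from a single covariate needs both inputs at their maximum. In the one-covariate simulation, the coverage ranges as written and with fixed effects overlap slightly.

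**A reader might also fault the plan because nothing follows from its balance check.** The plan says "Baseline comparisons will be examined using standardized mean differences" and sets no threshold. That is not a defect. For an unmatched covariate with no true difference and 109 per arm, the chance that the SMD exceeds 0.1 in absolute value is 2 × (1 − Φ(0.1/√(2/109))) = 0.46. A trigger would often fire by chance. Fixing the adjustment set in advance is the better course, and reporting SMDs descriptively is consistent with it.

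**Conclusion.** The point holds as an omission in the adjustment set. Duration and glucose-lowering medication are planned baseline data, the comparison is non-randomised, and the specific list in 2.6.2 leaves both unadjusted. It should be fixed; it does not invalidate the design.

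Under the central assumptions the bias is 0.09 HbA1c points, about 22% of the planned half-width, with 92.7% coverage. The plausible range runs from negligible to serious. It depends on the imbalance, on the strength of association with HbA1c change, on whether the two variables act together or against each other, and on their correlation with the matched variables. None of these is given.

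Two stronger conclusions are not supported. A reader might infer that the primary estimate will favour the app, but nothing in the documents fixes the direction. A reader might also treat the difference in care setting as part of this point. It is a separate matter: 2.2.4 discloses and justifies the specialty-clinic comparator, and the share of primary-care starts is unsettled because 3.2.1 lists only diabetes outpatient and inpatient settings while 3.1 and 5.1.1 include primary care.

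**What to change.** Before matching, and before any follow-up HbA1c is opened:

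1. Confirm that diabetes duration and baseline glucose-lowering medication can be extracted from the control EMR.
2. State in 2.6.2 that duration, baseline glucose-lowering medication (for example, number of agents), race and comorbidity count enter the linear mixed model as prespecified fixed effects. Keep the four-variable score and all its pairs.

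Putting the four added variables into the score is an acceptable alternative if match counts allow. In simulation the four-variable and eight-variable scores gave mean pairs of 107 against 104–106 with 600 controls, 104 against 96–98 with 300, and 98 against 87–91 with 200. At SD 1.5 the half-width is 0.398 with 109 pairs, 1.96 × 1.5 × √(2/98) = 0.420 with 98, and 0.443 with 88. The fixed-effect route avoids this loss.

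The cost is a few sentences in 2.6.2, extra fields in the control EMR query, and a half-width wider by less than 0.01 in the simulation. The main practical risk is missing values in controls, which could remove patients from the model fit, so completeness should be checked at step 1.
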